### **5.3. Beeper Feature**

The Beeper in the PGs provides: (1) an audible patient warning when potential therapy failure is detected between scheduled PG checks with an HCP, and (2) audible feedback to HCP regarding the state of the PG such as, current tachycardia mode and when charging for shock therapy. The Beeper may no longer be audible following an MRI scan. Loss of Beeper volume cannot be recovered.

**It is strongly recommended that an in-clinic follow-up schedule of every three months after an MRI scan to monitor device performance.**

## **6. Conditions of Use**

The following MRI Conditions of Use must be satisfied as listed here and in the *BSC MRI Technical Guide*. Where differences exist between the *BSC MRI Technical Guide* and the EN MR ICD study protocol, the protocol extends the *BSC MRI Technical Guide*.

### **6.1. Cardiology**

1. Patient is implanted with an ImageReady MR Conditional Defibrillation System
2. No other active or abandoned implanted devices, components, or accessories present

such as lead adaptors, extenders, leads, or pulse generators

3. Pulse generator is in MRI Protection Mode during scan
4. The patient must be continuously monitored by electrocardiography (ECG) during MR scan.  
Ensure backup therapy is available (external rescue).
5. Patient is judged to be clinically capable of tolerating no Tachycardia protection.
6. Patient does not have elevated body temperature or compromised thermoregulation at time of scan.
7. Pulse generator implant location restricted to left or right pectoral region
8. At least six (6) weeks have elapsed since implantation and/or any lead revision or surgical modification of the MR Conditional Defibrillation System
9. No evidence of a fractured lead or compromised pulse generator-lead system integrity

## **6.2. Radiology**

1. MRI magnet strength RF field Maximum spatial gradient MRI equipment specification	1.5 T only Approximately 64 MHz 20T/m (2,000 G/cm) Horizontal, 1H proton, closed bore scanners only
2. Specific Absorption Rate (SAR) limits for the entire active scan	Normal Operating Mode a : 

• Whole body averaged, <math>\leq 2.0</math> watts/kilogram (W/Kg)

• Head, <math>\leq 3.2</math> W/Kg

3. Maximum specified gradient slew rate	$\leq 200$ T/m/s per axis
4. The use of receive-only coils is not restricted. Local transmit-only coils or local transmit/receive coils may be used, but should not be placed directly over the defibrillation system.	
5. Patient in supine or prone position only	
6. Patient must be continuously monitored by electrocardiography (ECG) for the entire duration MR scan. Ensure backup therapy is available (external rescue).	

a. As defined in IEC 60601-2-33, 201.3.224, 3rd Edition.

## **7. Objectives**

The objective of the study is to observe the safety and effectiveness of the ImageReady MR Conditional Defibrillation System when used in the 1.5T MRI environment under the labeled Conditions of Use in a Chinese population.

## **8. Endpoints**

### **8.1. Primary Safety Endpoint**

- MR Scan-related ImageReady System Complication-Free Rate between the MR Scan and the MRI + 1 Month Visit

### **8.2. Primary Effectiveness Endpoints**

1. Abnormal increase in RV shocking impedance from the pre-MR scan to the 1 Month post-MR scan
2. Increase in RV pacing threshold (at 0.5ms) from the pre-MR scan to the 1 Month post-MR scan
3. Decrease in RV sensed amplitude from the pre-MR scan to the 1 Month post-MR scan
4. Increase in LV pacing threshold (at 0.5ms) from the pre-MR scan to the 1 Month post-MR scan
5. Decrease in LV sensed amplitude from the pre-MR scan to the 1 Month post- MR scan

### **8.3. Ancillary Assessments**

1. Assessment of RV and LV impedances
2. Assessment of RA lead measurements
3. Assessment of VT/VF episodes post-MR-scan
4. Assessment of programming the MRI Protection Mode
5. Assessment of Image Artifacts for non-medically necessary MR scans.

The MR ICD study referenced FDA IDE trial ENABLE MRI. The major difference is that ENABLE MRI will collect 25 episodes of VT/VF events post MR scan, while the small sample size MR ICD study would use shocking impedance measurement to evaluate the

integrity of the shocking circuit. The MR ICD study will also assess any VT/VF event post MR scan.

## **9. Design**

[figure not shown]
The MR ICD study is a multi-center, prospective, single –arm study in China. Phase I is completed when all the subjects finish MRI + 1 Month Visit, and the data will be summarized to support product CFDA registration. All subjects will be followed-up till 1 year post implantation.

### **9.1. Scale and Duration**

The MR ICD study will enroll 20 subjects at approximately 5 investigator centers in China, including 10 ICDs (with at least 2 single chamber ICDs and 2 dual chamber ICDs) and 10 CRT-D. The PGs will be DYNAGEN series and there is no further requirement for leads (see Table 5-1).

Data will be collected from subjects upon enrollment into the study, at implant, and at pre-discharge. Subjects will have an MR scan at 6-9 weeks post-implant, or at least 6 weeks after any required surgical interventions to the ImageReady System (labeled as MRI Visit). Subsequently, there will be a clinic follow up at MRI + 1 Month Visit, and recommended clinic follow up every 3 months post MR scan. Subjects will also be followed at 1 year post-implant, see Figure 9-1.

The MR ICD study is composed of two phases. Phase I is completed when all the subjects finish MRI + 1 Month Visit, which starts Phase II till 1 year post implantation. Phase I is expected to last about 9 months after first subject enrollment, and the whole study is expected to last about 20 months after first subject enrollment.

**Figure 9-1 MR ICD study Design**

## 9.2. Justification for the Study Design

BSC is conducting a global multi-center study, ENABLE MRI (NCT02652481), on MR conditional systems including DYNAGEN and INOGEN. The study will enroll 500 subjects, to confirm the safety and effectiveness of the ImageReady™ MR Conditional Defibrillation System when used in the 1.5T MRI environment under the labeled Conditions of Use. CFDA requires certain clinical trial in China to support the approval of ImageReady™ MR conditional defibrillation system.

The MR ICD study referenced ENABLE MRI. The major difference is that ENABLE MRI will collect 25 episodes of VT/VF events post MR scan, while the small sample size MR ICD study would use shocking impedance measurement to evaluate the integrity of the shocking circuit. The MR ICD study will also assess any VT/VF event post MR scan.

The MR ICD study is composed of two phases. Phase I is completed when all the subjects finish MRI + 1 Month Visit, and the data will be summarized to support product CFDA registration. All subjects will be followed-up till 1 year post implantation.

## **10. Subject Selection**

### **10.1. Study Population and Eligibility**

Subjects enrolled in the MR ICD study shall be selected from the investigators general patient population indicated for an ICD or CRT-D implantation. The Investigator is responsible for screening potential subjects and selecting those who meet the eligibility criteria for the study as described in Sections 10.2 and 10.3.

### **10.2. Inclusion Criteria**

Subjects who meet all of the following criteria may be given consideration for inclusion in this clinical investigation, provided no exclusion criteria are met (see 10.3).

1. Subject is indicated to Class I/II indications per guidelines/consensus released by Chinese Society of Cardiac Pacing and Electrophysiology
2. Subject must have the ImageReady System as their initial (de novo) defibrillation system implant
3. Subject will receive an ICD or CRT-D pulse generator in the left or right pectoral region ICD
4. Subject is able and willing to undergo an MR scan
5. Subject is willing and capable of providing informed consent and participating in all testing/ visits associated with this clinical study at an approved clinical study center and at the intervals defined by this protocol
6. Subject is age 18 or above

### **10.3. Exclusion Criteria**

Subjects who meet any one of the following criteria will be excluded from the MR ICD study.

1. Subject has other active or abandoned implanted cardiac rhythm devices, components or accessories present such as pulse generators, leads, lead adaptors or extenders

2. Presence of metallic objects that represent a contraindication to MR imaging at the discretion of the Radiologist and impacting the ability to conduct the study protocol
3. Subject needs or will need a medically necessary MR scan, before completing the 1-month post-MR follow-up visit
4. Subject is not clinically capable of tolerating the absence of Tachycardia therapy support for the duration that the pulse generator is in MRI Protection Mode, per Physician discretion
5. Subjects currently requiring dialysis
6. Subject has a mechanical heart valve
7. Subject has a known or suspected sensitivity to dexamethasone acetate (DXA)
8. Subject is currently on the active heart transplant list
9. Subject has documented life expectancy of less than 12 months
10. Subject is enrolled in any other concurrent study that might interfere with this study
11. Women of childbearing potential who are or might be pregnant at the time of this study

## **11. Subject Accountability**

### **11.1. Enrollment**

Subjects will be considered enrolled into the MR ICD study at the time of informed consent form execution. All subject enrollments will be counted against the enrollment ceiling for the study.

### **11.2. Withdrawal**

All subjects enrolled in the clinical study (including those withdrawn from the clinical study or lost to follow-up) shall be accounted for and documented. If a subject withdraws from the clinical investigation, the reason(s) shall be reported. If such withdrawal is due to problems related to investigational device safety or performance, the investigator shall ask for the subject's permission to follow his/her status/condition outside of the clinical study.

Reasons for withdrawal include, but are not limited to: subject not receiving a protocol required defibrillation system, physician discretion, subject choice to retire consent, loss to

follow-up, or death. While study withdrawal is discouraged, subjects may withdraw from the MRI ICD Study at any time, with or without reason, and without prejudice to further treatment. All applicable case report forms up to the point of subject withdrawal must be completed. Additional study data may no longer be collected after the point at which a subject has been withdrawn from the study or withdraws his/her consent, for whatever reason. All open adverse events should be closed or documented as chronic. Data collected up to the point of subject withdrawal may be used.

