### **24.2.Criteria for Premature Termination of the Study**

Possible reasons for premature study termination include, but are not limited to, the following.

- Important information that impacts the progression of the study (e.g. safety or production performance).
- Regulatory authorities decide to terminate the study.
- A decision on the part of Boston Scientific to suspend or discontinue development of the device.
- An enrollment rate far below expectation that prejudices the conclusion of the study.

Note: According to requirements in section[21](#), even if the MR ICD study is terminated, subjects with study device(s) shall be followed up for AE, SAE, SADE and device deficiency, which are to be assessed and reported.

There is no hypothesis testing or interim analysis in this study. If the study is terminated prematurely, the already collected data shall be described according to section[13](#).

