#### **24.5 Criteria for Suspending/Terminating a Study Site**

Boston Scientific Corporation reserves the right to stop the inclusion of subjects at a study site at any time after the study initiation visit if no subjects have been enrolled for a period beyond 3 months after site initiation, or if the site has multiple or severe protocol deviations/noncompliance without justification and/or fails to follow remedial actions.

In the event of termination of site participation, all study devices and testing equipment, as applicable, will be returned to BSC unless this action would jeopardize the rights, safety or well-being of the subjects. The EC and regulatory authorities, as applicable, will be notified. All subjects enrolled in the study at the site will continue to be followed till end of the study. The Principal Investigator at the site must make provision for these follow-up visits unless BSC notifies the investigational site otherwise.

According to section21, all subjects with study device(s) shall be followed up for AEs, which are to be assessed and reported. The Principal Investigator at the site must make provision for these follow-up visits unless BSC notifies the investigational site otherwise.

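### Section 11.2 ends study data collection at any withdrawal, even with consent intact, so a new complication in a scanned subject after withdrawal would not be counted

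*Combined protocol and SAP*

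**What the plan says.** Protocol Section 11.2 sets one rule for two situations: "Additional study data may no longer be collected after the point at which a subject has been withdrawn from the study or withdraws" consent. The sentence closes by applying this whatever the reason. The listed reasons show that withdrawal need not come from the subject: "Reasons for withdrawal include, but are not limited to: subject not receiving a protocol required defibrillation system, physician discretion", among others.

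For withdrawals caused by device safety or performance problems, Section 11.2 adds that "the investigator shall ask for the subject's permission to follow his/her status/condition outside of the clinical study". On events already known at withdrawal it says: "All open adverse events should be closed or documented as chronic. Data collected up to the point of subject withdrawal may be used".

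Other parts of the protocol provide follow-up for other groups:

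- Section 11.3: Attempt and Partial Implant subjects are followed for adverse events to 30 ± 7 days, and only then withdrawn.
- Section 24.2 (study termination): "even if the MR ICD study is terminated, subjects with study device(s) shall be followed up for AE, SAE, SADE and device deficiency".
- Section 24.5 (site termination): "all subjects with study device(s) shall be followed up for AEs, which are to be assessed and reported". Like 24.2, it attributes this to Section 21.
- Section 21.4, Table 21-3: events are reported to the end of the study. Individually withdrawn subjects are not mentioned.

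On analysis, Section 13.1.1 takes all subjects whose scan sequences were initiated as the safety data set, excludes missing data, and calls up to 2 failures reasonable. Section 13.4.3 repeats the exclusion of missing data, and SAP Section 7.3 rules out imputation for missing data.

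**The concern.** Stopping collection when a subject withdraws consent is proper. Stopping it when the investigator withdraws a subject who still consents is the plan's own choice, and no reason is given for it. The follow-up offered after a device-related withdrawal is outside the study, and no route is described by which its findings would reach the database, the Clinical Events Committee or the endpoint.

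The primary safety endpoint runs from the scan to MRI + 1 Month, a window that closes 23 to 37 days after the scan. If a scanned subject is withdrawn inside that window and then has a new complication, the plan has no means of recording it. The error runs one way: an unrecorded complication can only make the complication-free rate look better. With about 20 subjects and a limit of 2 failures, a single event can matter. Events after the window do not touch the primary endpoint but would be absent from the one-year adverse event reporting.

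**Working it through.** **1. Who is followed for adverse events after leaving the normal schedule**

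| Situation | Protocol section | Recorded adverse event follow-up |
|---|---|---|
| Attempt or Partial Implant (no study scan) | 11.3 | Yes, to 30 ± 7 days |
| Whole study terminated, subject has a device | 24.2 | Yes |
| Site terminated, subject has a device | 24.5 | Yes |
| Scanned subject withdrawn individually, consent intact | 11.2 | None in the study |

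The last row is the gap. These subjects have had the exposure under study and have the least follow-up provided.

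**2. The plan's own figure**

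Sections 11.4 and 13.3: 10 enrolled per group less at most 2 lost = 8 per group, and 2 × 8 = 16 in total. This reproduces. Both sections define the 8 as subjects who complete the scan sequences; only the synopsis speaks of inclusion in the final analysis. A subject withdrawn after a completed scan therefore still counts toward the 8, and would not trigger the expansion of enrolment that those sections allow.

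**3. Effect on the safety endpoint (illustration)**

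Assumptions: all 20 subjects are scanned; *w* are withdrawn before MRI + 1 Month and excluded as missing; *f* failures are observed among the rest; in the worst case each withdrawn subject has one unseen complication. The plan gives no value for *w*.

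- Reported rate = (20 − w − f) / (20 − w)
- Worst-case rate = (20 − w − f) / 20
- Worst-case failures = f + w, compared with the limit of 2

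| w | f | Reported rate | Worst-case rate | Worst-case failures | Within limit of 2? |
|---|---|---|---|---|---|
| 0 | 2 | 18/20 = 90.0% | 90.0% | 2 | Yes |
| 1 | 0 | 19/19 = 100% | 95.0% | 1 | Yes |
| 1 | 2 | 17/19 = 89.5% | 85.0% | 3 | No |
| 2 | 1 | 17/18 = 94.4% | 85.0% | 3 | No |
| 3 | 0 | 17/17 = 100% | 85.0% | 3 | No |

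One unseen complication is enough to pass the limit if 2 failures are already observed; three are needed if none are.

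If a withdrawn subject were instead kept in the denominator as event-free, the case w = 1, f = 2 would be reported as 18/20 = 90.0%. The unseen failure is missed either way.

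**4. Precision**

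With no observed failures, the two-sided 95% Clopper-Pearson lower limit is 83.2% at n = 20 and 79.4% at n = 16. The interval widens as subjects drop out, but it does not reflect that the missing outcomes may be worse.

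**5. Follow-up beyond the primary window**

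For a subject scanned 42 to 63 days after implant, the time from the scan to the nominal one-year visit is 365 − 63 = 302 to 365 − 42 = 323 days. That is the most one subject's recorded follow-up could lose.

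**The case against.** Several stronger readings are tempting, and the documents do not support them.

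- **That Sections 24.2 and 24.5 contradict 11.2.** They do not. Section 24.2 covers termination of the study. Section 24.5 covers termination of a site, where enrolled subjects remain in follow-up to the end of the study. Neither deals with individual withdrawal. What can be said is that their broad wording about subjects with study devices is not reconciled with 11.2.
- **That events in withdrawn subjects are lost altogether.** A device problem that leads to withdrawal happens before it. Section 11.2 requires the case report forms to be completed to that point and allows those data to be used, and Table 21-3 requires serious adverse events to be reported within 24 hours. Such an event can still be adjudicated and counted. Only what happens after withdrawal is missed.
- **That a lost subject uses up part of the 2-case limit.** The limit counts failures, not losses. The two coincide only under the worst-case assumption above.
- **That effectiveness data suffer most when withdrawal is for a device problem.** Subjects with a lead-related complication between the MRI Visit and MRI + 1 Month are already excluded from all five effectiveness data sets, so a further check would restore nothing for them.

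It is also fair to say that the exposed group is narrow. No rule requires withdrawal of a scanned subject. Harm to the primary endpoint needs a discretionary withdrawal with consent intact, within about a month of the scan, followed by a new complication. The consent form is not in the material available for review, so what subjects agree to after withdrawal cannot be checked.

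All of this limits the size of the point. It does not explain why obtainable safety data from a consenting, scanned subject should go uncollected.

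**Conclusion.** The point holds as a gap in follow-up. Section 11.2 ends in-study data collection for any withdrawn subject, without separating withdrawal of consent from withdrawal by the physician. Combined with the exclusion of missing data, this means a new complication after withdrawal and before MRI + 1 Month cannot count in the primary safety endpoint, and later events drop out of adverse event reporting.

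The likely size is small and may be nil, because the plan gives no expected number of such withdrawals. In the worst case it decides the result: with 2 observed failures among 20 scanned, one unseen complication takes the count to 3. That figure assumes all 20 are scanned and that the withdrawn subject has a complication judged related to the scan. This is a cheap improvement to make, not a flaw that undermines the study.

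**What to change.** Reword Section 11.2 along these lines:

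> Study data collection stops only when the subject withdraws consent to it. A subject withdrawn for any other reason who still consents remains in the study database for adverse events, serious adverse events, device deficiencies and death, at least through the MRI + 1 Month window and preferably to Implant + 1 Year. If the subject has been scanned and agrees, the scheduled MRI + 1 Month evaluation is also recorded.

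In addition:

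- Record the type of withdrawal (consent withdrawn, or other) in the eCRF.
- Apply the same in-study route to subjects withdrawn for device safety or performance who permit follow-up.
- Reconcile Section 11.2 with Sections 21 and 24, so that individually withdrawn subjects with a study device are named.
- State in the SAP how a scanned subject withdrawn before MRI + 1 Month is counted in the safety endpoint, and show the worst-case count beside the main result.

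Cost: a protocol amendment, one eCRF field, matching consent wording, and a few extra follow-up contacts. The 1-month evaluation is already a scheduled visit.

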### **11.3. Subject Status and Classification**

Subjects enrolled in the MR ICD study will be placed into one of four classifications, as defined below.

**Intent** - Intent refers to a subject who has been enrolled, but does not have the lead(s) or PG introduced into their body. There are no follow-up requirements for intent subjects. The original informed consent form (ICF) for intent subjects should be maintained in the Center's files.

**Attempt** - Attempt refers to a subject who has had the lead(s) and/or PG introduced into the body, but is not successfully implanted with any portion of the ImageReady System during the implant procedure. Attempt subjects must be followed  $30 \pm 7$  days post-attempted ImageReady System implant to assure there are no associated adverse events, or to assure the resolution of any adverse events associated with the attempted ImageReady System implant, then withdrawn from the study.

**Partial Implant** - Partial Implant refers to a subject who is implanted with a component of the ImageReady System (lead or pulse generation) during the implant procedure, but does not end up with a complete ImageReady System. They shall not receive the protocol required MR Scan according to the *BSC MRI Technical Guide*. Partial Implant subjects must be followed  $30 \pm 7$  days post- ImageReady System implant to assure there are no associated adverse events, or to assure the resolution of any adverse events associated with the ImageReady System implant, then withdrawn from the study.

**Implant** - Implant refers to a subject who is successfully implanted with the ImageReady System per the study protocol. These subjects are followed in accordance with the follow-up

schedule and included in all analyses of safety and performance.

